### 8 STUDY POPULATION

Unless otherwise stated, all study population analyses will be performed on the Safety Population.

#### 8.1 SUBJECT DISPOSITION

Subject disposition will be presented for all subjects. The composition of the analysis populations and those who were screen fails, enrolled, completed or discontinued from the study will be summarized by dose cohort and overall with descriptive statistics. Reasons for early discontinuation will be presented with frequencies and percentages for all categories.

The frequency and percentage of subjects who are screen fails, subjects who receive at least one dose of BVD-523 or not, subjects who have completed the study as per protocol or not, and subjects who withdrew prematurely from the study with their reasons for discontinuation (death, anaphylaxis, withdrawal of informed consent, disease progression, unacceptable toxicity, change in the subject's condition that renders the subject unacceptable for further treatment in the special treatment of PI, at least 3 interruptions of BVD-523 intake of >7 days each, or 8 consecutive days, subject becomes pregnant, subject is lost to follow-up, or other) will be summarized by treatment group and overall (all treatment groups combined) separately for Study Parts 1 and 2. The total number of mITT subjects in each treatment group for each study part will be used as the denominator for the calculation of percentages.

The number and percentage of subjects in each of the analysis populations as specified in Section 5 will also be tabulated similarly.

A listing of analysis population, study completion, and early termination with the primary reason for early withdrawal will also be provided.

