#### 5.1 SCREENED

The Screened Population will consist of all patients who have signed the informed consent. The screened population will be used for disposition tables.

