#### 5.3 MODIFIED INTENT-TO-TREAT

The modified Intent-to-Treat (mITT) Population will consist of all subjects who have a screening visit / sign the informed consent and had no screening failures/were eligible for treatment regardless of whether or not they have received treatment. Demographic and baseline characteristics will be tabulated for the mITT population. Additionally, the mITT population will be used for calculating response in Part 2.

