## 14.1 DEMOGRAPHICS SUMMARY FIGURES AND TABLES

#### Part II

## **Part II: Study Population**

Table	Title	Population
Part II - Table 14.1.1.1	Summary of Analysis Populations	Enrolled Population
Part II - Table 14.1.1.2	Subject Disposition	Screened Population
Part II - Table 14.1.2	Protocol Deviations	Screened Population
Part II - Table 14.1.3.1	Demographic and Baseline Characteristics	Safety Population
Part II - Table 14.1.3.2	Demographic and Baseline Characteristics	mITT Population
Part II - Table 14.1.3.3	Demographic and Baseline Characteristics	PP Population
Part II - Table 14.1.4.1	Medical History	Safety Population
Part II - Table 14.1.4.2	Previous Cancer Surgery	Safety Population
Part II - Table 14.1.4.3	Previous Stem Cell Transplant	Safety Population
Part II - Table 14.1.4.4	Transfusion/Blood Product Use	Safety Population
Part II - Table 14.1.4.5	Prior MEK Therapies	Safety Population
Part II - Table 14.1.4.6	Previous Therapies	Safety Population
Part II - Table 14.1.5	On Study Procedures	Safety Population
Part II - Table 14.1.6.1	Prior Medications	Safety Population
Part II - Table 14.1.6.2	Concomitant Medications	Safety Population
Part II - Table 14.1.6.3	Concomitant Medications Taken for Adverse Events	Safety Population
Part II - Table 14.1.7.1	Treatment Compliance	Safety Population
Part II - Table 14.1.7.2	Exposure to Study Drug	Safety Population
Part II - Table 14.1.8	Pregnancy Test Results	Enrolled Population

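### SAP 8.1 expresses screen failures as a percentage of the mITT count, a set that SAP 5.3 defines to exclude them

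*SAP*

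**What the plan says.** SAP 8.1 (Subject Disposition) opens by saying that disposition covers all subjects. It then lists what is to be summarised by treatment group and overall, separately for each study part: "The frequency and percentage of subjects who are screen fails, subjects who receive at least one dose of BVD-523 or not", followed by completion and by premature withdrawal with reasons. One sentence sets the divisor, with no exception for any row: "The total number of mITT subjects in each treatment group for each study part will be used as the denominator". The next paragraph says that counts and percentages for the Section 5 analysis populations are to be produced in the same manner.

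Three other places bear on this:

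- SAP 5.3 (Modified Intent-to-Treat) admits consented subjects only if they "had no screening failures/were eligible for treatment regardless of whether or not they have received treatment".
- SAP 5.1 (Screened) states: "The Screened Population will consist of all patients who have signed the informed consent". It adds: "The screened population will be used for disposition tables".
- SAP 14.1 lists Table 14.1.1.2, Subject Disposition for Part 2, against the "Screened Population".

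Protocol 10.2.2 defines mITT more broadly, as everyone with a screening visit or a signed consent. It does not remove screen failures.

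**The concern.** A percentage in a disposition table should be a part of a whole. Under SAP 8.1 read with SAP 5.3, the screen failures in the numerator cannot appear in the denominator. The printed figure is therefore not a screen-failure rate, though it would be labelled as one.

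A programmer working from 8.1 and one working from 5.1 and the table list would also print different figures for the same row, and nothing in the SAP says which text governs.

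What is at stake is descriptive. In a small, single-arm, open-label study, the screen-failure rate tells the reader how selected the treated patients are. An inflated figure, or one above 100%, would have to be corrected or explained when the study is reported.

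**Working it through.** There is no stated screen-failure percentage to reproduce, so the check is of definitions followed by ratio arithmetic.

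**Inputs**

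- M = number in mITT (SAP 5.3).
- F = number of screen failures. The documents do not give this; the values below are assumptions.
- S = number screened (SAP 5.1). I take S = M + F, which assumes that every consented subject is either a screen failure or eligible.
- M = 40 for Part 2, from the planned size in SAP Section 4. This assumes that the planned 40 become the mITT count.

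**Step 1: what each rule computes.** SAP 8.1 gives F/M. SAP 5.1 and Table 14.1.1.2 point to F/S. With f = F/S, F/M = f/(1 − f), which is the odds of screen failure. F/M is larger than F/S for any F above zero, and exceeds 1 once F is greater than M.

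**Step 2: Part 2 illustration, M = 40.**

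| F (assumed) | SAP 8.1: F/M | Screened: F/S |
|---|---|---|
| 10 | 10/40 = 25.0% | 10/50 = 20.0% |
| 20 | 20/40 = 50.0% | 20/60 = 33.3% |
| 30 | 30/40 = 75.0% | 30/70 = 42.9% |
| 40 | 40/40 = 100.0% | 40/80 = 50.0% |
| 45 | 45/40 = 112.5% | 45/85 = 52.9% |

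**Step 3: independence from study size.** Because F/M depends only on f, assumed true rates of 10%, 20%, 30%, 50% and 60% print as 11.1%, 25.0%, 42.9%, 100.0% and 150.0% in either part.

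**Step 4: analysis-population counts.** If these take the same divisor, the Screened row is S/M = 1 + F/M. With M = 40 and F = 10, 20 or 30 it is 50/40 = 125%, 60/40 = 150% or 70/40 = 175%. One screen failure is enough to pass 100%.

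**Step 5: the remaining rows.** Subjects who were dosed or not dosed, who completed, or who withdrew can all be counted within mITT, since SAP 5.3 keeps eligible subjects whether or not they were treated. For these rows an mITT divisor gives a proper proportion.

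**Step 6: by-group reporting.** SAP 8.1 asks for the rows by treatment group. A Part 1 subject who fails screening may never be given a dose cohort, and a Part 2 subject may fail before RAS status is known. Some failures may therefore have no group to be counted in.

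**The case against.** The strongest reply is that SAP 5.1 and the table list say whom the table covers, while SAP 8.1 says what divides the counts. A table can show all screened subjects and still use mITT for the rows after enrolment. That stands for those rows, so a reader who inferred that every disposition percentage is wrong would go beyond the documents. It does not rescue the screen-failure row, because 8.1 makes no exception for it and 5.3 shuts those subjects out.

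Second, under the protocol's broader mITT definition in 10.2.2 the 8.1 rule would be coherent, because the divisor would contain the screen failures. That is a plausible origin of the sentence, and the SAP's table of contents, which has no entry for the Screened Population, fits a late change to Section 5. This is inference. The current SAP uses the narrower definition, and under it the rule fails.

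Third, frequencies are printed beside percentages, so a careful reader could recompute the rate. The table shells, which might show the intended divisor, are in a separate attachment that is not available here. Both points lower the weight, but neither corrects the stated rule.

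Fourth, a reader might infer that no screen failure can ever have a treatment group. The documents do not support that. RAS samples are taken at screening (Protocol 5.2.1), and RAS status is needed to confirm Part 2 eligibility (SAP 12.2), so a patient with known status who fails another criterion could be classified. The supportable statement is that some may have no group.

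Finally, a printed value above 100% for screen failures needs more failures than mITT subjects. The documents give no reason to expect this; it is possible, not predicted.

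**Conclusion.** The point holds as an internal inconsistency that makes a stated rule yield a wrong number. It is confined to the screen-failure row and, if the analysis-population counts follow the same rule, to the Screened row of that summary. The screen-failure figure is overstated whenever F is above zero: by 5 percentage points at 10 failures against 40 mITT subjects, about 17 at 20, and about 32 at 30. Those counts are assumptions; only the direction follows from the definitions.

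The arithmetic also rests on S = M + F. If some consented subjects are neither screen failures nor eligible, S is larger and the gap widens.

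It would be wrong to infer that any trial result is affected. The documents report no disposition figures, and DLT, MTD and response results do not depend on this divisor. The point is minor, and worth correcting because the correction is cheap.

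**What to change.** In SAP 8.1:

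- Report screen failures and the analysis-population counts as a percentage of the Screened Population, overall per study part, because screen failures may have no dose cohort or RAS group.
- Keep mITT as the denominator, by group, for dosed or not dosed, completed and withdrawn. The Safety Population would not serve for the dosed row, since everyone in it has been dosed and the row would always be 100%.
- Name the denominator for each row in the text and in the table shells.

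In the same revision, reconcile the mITT definition in SAP 5.3 with Protocol 10.2.2, since mITT is also used for response in Part 2. Align the label on Table 14.1.1.1 (Summary of Analysis Populations) as well: it cites an Enrolled Population that SAP Section 5 does not define.

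The cost is a few sentences in the SAP, the matching shell footnotes, and a decision on which mITT definition stands. No new data are needed.

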### 8.2 DEMOGRAPHIC AND BASELINE CHARACTERISTICS

Demographic and baseline characteristic data will be summarized with descriptive statistics for (including but not limited to): age, gender, race, AML or MDS subtype (including relapsed or refractory status), bone marrow molecular cytogenetics, RAS positive or negative status (optional for Part 1, required for Part 2), body weight and height, ECOG performance status, previous chemotherapy, and previous immunotherapy.

Demographic and baseline characteristics will be summarized descriptively by treatment group and overall for each study part using the Safety, mITT, and PP populations.

Demographic and baseline characteristics include, but are not limited to: age (years), gender, ethnicity, race, weight (kg), height (cm), Eastern Cooperative Oncology Group (ECOG) Performance Score, cancer type (AML or MDS), bone marrow cytogenetics, RAS mutation status, previous chemotherapy and previous immunotherapy. Age will be calculated in years from date of birth to the date of informed consent as an integer value.

Page 21

#### 8.3 PRIOR AND CONCOMITANT MEDICATIONS

Medications will be coded according to the World Health Organization Drug Dictionary (WHO Drug, March 2015). A summary of all medications will then be provided using the WHO Drug ATC classification and preferred term.

All medications taken except for BVD-523 will be classified into prior or concomitant medications.

- A prior medication is defined as any medication taken within 28 days prior to the initiation of BVD-523 irrespective of whether it is continued into the study.
- A concomitant medication is defined as any medication taken after the initiation of BVD-523 and up to 30 calendar days after the last administration of BVD-523.

If a medication falls into both prior and concomitant time phase then it will be presented in both time phases. All medications except for BVD-523 will be summarized by WHO Drug ATC classification and preferred term with regards to treatment groups for each study part and time phase.

At each level (WHO Drug ATC classification and Preferred Term) of summarization, a subject will be counted only once per drug class or preferred term. For example, if a subject reports multiple concomitant medications with the same drug class, then that drug class will only be incremented by one. Similarly, if a subject reports multiple concomitant medications with the same preferred term, then that preferred term will only be incremented by one. Whether medications are taken for AEs or not will also be provided. The medication with indication equals to the AE verbatim which also has "Concomitant Medications" as the response to the question of "Any Treatment Required?" will be deemed as the medication taken for the AE. Medications taken for AEs will be tabulated by WHO Drug ATC classification and preferred term with regards to treatment groups for each study part.

Subject listing of medications will also be presented by time phase.

#### 8.4 MEDICAL HISTORY

Medical history will be summarized with descriptive statistics by medical history code. A comprehensive data listing will also be included. Specific intervention of interest include prior cancer surgery related to AML or MDS, chemotherapy, immunotherapy, hormonal, radiation, stem cell treatment and MEK therapies.

## 8.4.1 Prior Cancer Surgery Related to AML or MDS

Prior cancer surgeries related to AML or MDS will be summarized by indication (diagnostic, therapeutic, or other) and time prior to enrollment into the trial. They will be summarized by descriptive statistics for each study part. A listing will also be provided in the order of occurrences within a subject.

### 8.4.2 Previous Chemotherapy

Previous chemotherapy information includes description/name of the chemotherapy, start/stop date, reason for therapy, best response from the therapy, total number of cycles completed, best

response, and reason for discontinuation. They will be summarized by descriptive statistics for each study part. A listing of previous chemotherapy information will also be provided in the order of occurrences within a subject.

### 8.4.3 Previous Immunotherapy

Previous immunotherapy data including type of immunotherapy/name (monoclonal antibodies, cancer vaccine, other immunotherapy), start/stop date, and reason for discontinuation (completed regimen, disease progression, other) will be listed by time of occurrence within a subject.

## 8.4.4 Previous Hormonal Therapy

Previous hormonal therapy including type, start/stop date, reason for therapy, best response for therapy, total number of cycles completed, and reason for discontinuation (completed regimen, disease progression, other) will be listed by time of occurrence within a subject.

## 8.4.5 Previous Radiation Therapy

Previous radiation therapy including type, total dose, delivery site, start/stop date, reason for therapy, best response for therapy, total number of cycles completed, and reason for discontinuation (completed regimen, disease progression, other) will be listed by time of occurrence within a subject.

## 8.4.6 Previous Stem Cell Therapy

Previous stem cell therapy including type, start/stop date, reason for therapy, best response for therapy, total number of cycles completed, and reason for discontinuation (completed regimen, disease progression, other) will be listed by time of occurrence within a subject.

#### 8.4.7 Previous Transfusion/Blood Product Use

Previous transfusion/blood product use blood product, date, amount transfused, and relevant test results (e.g. hemoglobin, platelets, or other) will be listed by time of occurrence within a subject.

### 8.4.8 Prior MEK Therapies

Prior MEK therapies including type, start/stop date, duration (days), reason for therapy, best response for therapy and reason for discontinuation (completed regimen, disease progression, other) will be listed by time of occurrence within a subject.

#### 8.5 INCLUSION/EXCLUSION CRITERIA

Inclusion and exclusion criteria failures will be included in a data listing.

#### 8.6 PROTOCOL DEVIATIONS

Protocol deviations will be summarized with descriptive statistics by cohort and category. All protocol deviations will be reported, but prior to generating Part 1 TFLs or Part 2 TFLs the list of protocol deviations will be reviewed and each classified as either major or minor. A listing of all events will also be included. Protocol deviation categories are:

- Inclusion/exclusion criteria
- Informed consent issue
- Out of window visit
- Protocol required evaluation not completed
- Physician decision
- Subject refused
- Prohibited medication
- Pharmacokinetic data
- Other

Impacts of the above protocol deviations on the analysis population will be determined by the study team before study closure and documented in the SAP.

The frequency and percentage of subjects with each protocol deviation along with the impact on the analysis population will be presented by treatment group and overall for each study part using the mITT Population. A listing of subjects with protocol deviation(s) will also be provided.

### 9 EFFICACY ANALYSIS

Unless otherwise stated, efficacy analyses will be performed on both the modified ITT and PP populations.

#### 9.1 PRIMARY ENDPOINT ANALYSIS

As this is a Phase 1/2 study, there is no formal primary efficacy endpoint.

The primary safety endpoints are the DLTs and MTD for BVD-523 administered alone in subjects with AML or MDS (Part 1) and preliminary efficacy (AML/MDS response) of BVD-523 administered at the RP2D dose in subjects with AML or MDS with or without RAS mutant positive disease (Part 2). The MTD and RP2D will be determined based upon the observed DLTs at each dose level as described in the protocol.

### 9.2 SECONDARY ENDPOINT ANALYSES

While no formal efficacy analyses will be conducted, secondary efficacy endpoints are:

- Pharmacokinetic (PK) profile of BVD-523 and selected metabolites
- Progression Free Survival (PFS) and Duration of Response (DOR) in subjects achieving Complete Response (CR) or Complete Response with incomplete platelet response (CRp)

## 9.2.1 PK profile

Pharmacokinetic analyses are discussed in Section 11 of this SAP.

## 9.2.2 Response

Subject response will be determined differently depending on disease type (MDS or AML).

**MDS** – The response criterion for evaluation of MDS is based on the International Working Group (IWG) criteria published in 2006.

Table 9.1 Table 3 from IWG 2006 MDS Response Criteria

Response	Peripheral Blood
Complete Response	Peripheral: Normal peripheral counts with persistent granulocyte count >=1.0*10 $^9$ /L, platelet count $\geq$ 100*10 $^9$ /L
(CR) [for 4 weeks]	Marrow: Normal bone marrow with persistent marrow blasts <=5%; persistent dysplasia will be noted
Partial Response (PR)	Peripheral: Normal peripheral counts with granulocyte count $\ge 1.0*10^9/L$ and platelet count $\ge 100*10^9$
[for 4 weeks]	Marrow: Normal bone marrow with marrow blasts >5% but were reduced by 50% or more
Marrow Complete Response (mCR) [for 4 weeks]	Reduction of bone marrow blasts to <=5% without normalization of peripheral counts
	Erythroid Response (HI-E): Major Response: Hemoglobin increase >=1.5g/dL or RBC transfusion independence
Hematological Improvement (HI) [for at least 8 weeks]*	Platelet Response (HI-P): Major Response: Absolute increase of platelet count <20 to >20*10°/L and by at least 100%, or if more than 20*10°/L, by an absolute increase of at least 30**10°/L
	Neutrophil Response (HI-N) : Major Response: Granulocyte increase >=100%, and by an absolute increase ≥0.5*10°/L
Less than Partial Remission**	

\*Abnormal baseline counts were the averages of at least two measurements over at least one week prior to therapy, not influenced by transfusions.

\*\*Added as a response option in Note to File dated 21JUL2015.

21 2000111201 2011

AML – The response criteria for AML will be based on the modified recommendation of the International Working Group (IWG) published in 2003. Information regarding transfusion dependence will be noted as a visit assessment and space provided in the eCRF.

Table 9.2 Table 4 from IWG 2003 AML Response Criteria

Response	Peripheral Blood	Bone Marrow
Complete Remission (CR)	ANC > $1.0 \times 10^9$ /L, Platelets $\geq 100 \times 10^9$ /L, independence from red cell and platelet transfusions over the past week	≤ 5% blasts
Complete Remission with Incomplete Platelet Recovery (CRp)	ANC > 1.0 x 10  /L, Platelets < 100 x 10  /L, independence from red cell transfusions over the past week	≤ 5% blasts
Complete Response with Incomplete Blood Count Recovery (Cri)	ANC $< 1.0 \times 10^9/L$	≤ 5% blasts
Partial Remission (PR)	ANC $> 1.0 \times 10^9$ /L, Platelets $\ge 100 \times 10^9$ /L	Decrease of ≥ 50% in blasts to level of 5% to 25%
Less than Partial Remission*		

ANC = absolute neutrophil count

#### 9.3 OTHER EFFICACY ANALYSES

There are no other efficacy analyses.

#### 9.4 INTERIM ANALYSIS

There will not be a formal interim analysis; however, TFLs will be generated for Part 1 after a MTD is determined; i.e. as Part 2 is ongoing.

#### 10 SAFETY

Safety analyses will be performed using the Safety Population. Safety will be assessed by examining all adverse events reported during the study including the incidence, and relationship to BVD-523. In addition, safety evaluations will be conducted at Baseline, Days 1, 8, 15, 22, 29, 36, 43, and, in subjects who continue treatment, every 3 weeks or if clinically indicated thereafter. These evaluations will include a targeted ECG where clinically warranted, and clinical laboratory analytes (hematology, chemistry, urinalysis and pregnancy test). An ophthalmologic assessment will also be conducted at baseline, at the end of study and at other visits by an ophthalmologist if clinically indicated.

\*Added as a response option in Note to File dated 21JUL2015

### 10.1 EXPOSURE TO STUDY DRUG

All exposure and compliance data will be provided in data listings.

Descriptive statistics will be provided for the total (cumulative) doses taken and total duration of treatment by treatment group for each study part. The total duration of treatment is calculated as (treatment stop date – treatment start date) + 1. If treatment stop date is missing, the date of final clinic visit will be used. By subject listing of study drug exposure will also be presented by study part and treatment group for each treatment cycle and all cycles combined. Treatment compliance is accessed by reviewing pill count. Patient frequencies will be provided for the summary of treatment compliance.

